8.2.8. Abdominal Examination

An abdominal examination for hepatomegaly will be performed as described in the SoA ([Table 1](#)).

8.2.9. Interim Follow-up Contact

After the completion of Month 24 visit, follow-up contacts (eg, phone calls) every 6 months (± 1 month) will be placed in between the on-site visits (at Months 30, 42 and 54) to review general health status, including safety and bleeding episodes as well as any FVIII concentrate usage. If the initial contact attempt is unsuccessful, a minimum of 3 contact attempts must be documented before the interim follow-up can be considered unsuccessful. AEs and concomitant medications should be reviewed and captured as per Sections [8.3](#) and [6.5](#), respectively.

Telephone contacts are not required if they fall when a participant is due on site for a blood draw.

8.2.10. Suicidal Ideation and Behavior Risk Monitoring

Not applicable for this study.

8.2.11. Pregnancy Testing

Not applicable for this study.

8.2.12. Rater Qualifications

Not applicable for this study.

8.2.13. Immunogenicity Assessments

Blood samples for immunogenicity assessments will be collected as outlined below.

8.2.13.1. AAV2/6 Antibodies

Samples for neutralizing activity to AAV capsid proteins (neutralizing antibodies) will be collected at screening to determine eligibility for the study. It is recommended to perform the other screening tests only if the AAV2/6 neutralizing activity results are acceptable. The neutralizing activity is to be reassessed if the screening period takes more than 8 weeks.

Samples will also be collected to assess both total and neutralizing antibodies to AAV2/6 over time, as displayed in the SoA ([Table 1](#)).

8.2.13.2. FVIII Inhibitor Titer

FVIII inhibitor levels will be measured as displayed in the SoA ([Table 1](#)). Weekly assessments (through Week 52) may be required if a participant is receiving steroids or develops an inhibitor. After Week 52, measurement of FVIII inhibitor titer may increase if warranted by changes in FVIII activity or the presence of inhibitor.

8.2.13.3. Interferon-Gamma ELISPOT

Samples for Interferon-gamma ELISPOT will be collected to detect a proliferation of capsid-specific T cells at baseline and Week 6 (± 3 days). Additional samples will be collected if there is a 50% drop in Factor VIII expression and/or prior to initiation of a corticosteroid treatment if possible.

8.2.14. Optional Liver Biopsy

An optional liver biopsy can be performed (in participants who consent to do so and as per investigator's judgement) during the postinfusion period until year 5 i.e, the end of the study. The procedure may be repeated once, later in the study, to assess evolution over time (in participants who consent to do so and as per investigator's judgement).

This substudy may be proposed to any participant, unless there is a condition that, in the opinion of the investigator or a hepatologist or radiologist, would make liver biopsy contraindicated.

The exploratory objectives of the substudy are to evaluate vector integration in the liver, the histopathology of the liver tissue and to assess the expression of protein and/or RNA levels of FVIII and other biomarkers of interest in the liver (depending on collected material). A biopsy will be made upon investigator's decision; it can be performed at any time postinfusion to assess liver health, integration and FVIII in the liver, but could also be triggered by sustained elevated FVIII activity levels, by a significant FVIII activity decline, by a sustained ALT elevation $>$ ULN or to assess the long-term gene therapy effects on the liver.

Any participant who consents to the procedure will have a liver biopsy via either transjugular or percutaneous (ultrasound-guided) route, according to the standard procedures of the institution. At least 2 tissue cores will be harvested and additional details for collecting and handling the biopsy specimens are provided in the Laboratory Manual.

FVIII activity levels should be assessed within 7 days before the biopsy and on the day of the biopsy, prior to the procedure. It is recommended that participants have a FVIII activity level of $\geq 50\%$ (or higher, depending on local guidelines and/or investigator discretion) when doing the procedure. As needed, participants may be treated with additional exogenous FVIII replacement products in order to increase their FVIII activity levels to an appropriate level, under the supervision/instruction of the investigator, to ensure the safety of the participant during the procedure.

Participants consenting to the optional liver biopsy are recommended to undergo pre-biopsy assessments such as:

At least 28 days before the procedure:

- Physical examination
- Central laboratory safety panels (hematology and clinical chemistry, including LFTs) and hemostasis parameters
- Liver ultrasound (fasting recommended at least 8 hours prior to ultrasound)
- FibroScan or Fibrotest

At least 7 days before the procedure:

- Central and local FVIII activity level assessments
- Pre-biopsy consultation (with hepatologist and/or radiologist)

On the day of the biopsy before the procedure:

- Participants will be required to observe an 8-hour fasting period before the procedure.
- Brief physical examination
- Central and local laboratory safety panels (hematology and clinical chemistry, including LFTs) and hemostasis parameters
- Central and local FVIII activity level assessments
- As needed, participants may be treated with additional exogenous FVIII replacement products to increase their FVIII activity levels to an appropriate level.

The follow-up care should be done according to the local standard of care. If only a small amount of tissue (< 2 cm) is obtained at the time of the biopsy, the participant may be asked to consent for a second pass. In this case, the original < 2 cm sample should still be retained and handled according to the instructions for handling biopsy specimens in the Laboratory Manual.

Following completion of the biopsy, the participant should remain under observation in the hospital according to the local procedure. Overnight post-procedure observation may be done at the investigator's discretion and/or according to local guidelines.

Whenever applicable, any finding related to the optional biopsy should be further assessed and followed as clinically appropriate to manage the participant's medical care. A hepatologist and/or other specialist clinicians should be consulted if required. Additional liver ultrasound and/or FibroScan may be considered at the discretion of the investigator and/or hepatologist.

8.3. Adverse Events and Serious Adverse Events

The definitions of an AE or SAE can be found in [Appendix 3](#).

AEs will be reported by the participant (or, when appropriate, by a caregiver, surrogate, or the participant's legally authorized representative).

The investigator and any qualified designees are responsible for detecting, documenting, and recording events that meet the definition of an AE or SAE and remain responsible to pursue and obtain adequate information both to determine the outcome and to assess whether the event meets the criteria for classification as an SAE or caused the participant to discontinue the study intervention (see Section [7.1](#)).

Each participant will be questioned about the occurrence of AEs in a nonleading manner.

In addition, the investigator may be requested by Pfizer Safety to obtain specific follow-up information in an expedited fashion.

8.3.1. Time Period and Frequency for Collecting AE and SAE Information

The time period for actively eliciting and collecting AEs and SAEs (“active collection period”) for each participant begins from the time the participant provides informed consent, which is obtained before the participant’s participation in the study (ie, before undergoing any study-related procedure and/or receiving study intervention), through and including to the last visit (completion at 60 months [± 1 months]) or at ETV for participants who discontinue.

However, from Month 36 through to the end of study (Month 60), only the following AEs will be actively collected:

- SAEs
- Non-serious AEs determined to be related to study intervention by the investigator or where causality is unknown.

Follow-up by the investigator continues throughout and after the active collection period and until the AE or SAE or its sequelae resolve or stabilize at a level acceptable to the investigator and Pfizer concurs with that assessment.

For participants who are screen failures, the active collection period ends when screen failure status is determined.

If the participant withdraws from the study and also withdraws consent for the collection of future information, the active collection period ends when consent is withdrawn.

If a participant definitively discontinues or temporarily discontinues study intervention because of an AE or SAE, the AE or SAE must be recorded on the CRF and the SAE reported using the CT SAE Report Form.

Investigators are not obligated to actively seek AEs or SAEs after the participant has concluded study participation. However, if the investigator learns of any SAE, including a death, at any time after a participant has been discharged from the study, and he/she considers the event to be reasonably related to the study intervention or study participation, the investigator must promptly notify the sponsor.

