6. STUDY INTERVENTION

Study intervention is defined as any investigational intervention(s), marketed product(s), placebo, or medical device(s) intended to be administered to a study participant according to the study protocol.

For the purposes of this protocol, study intervention refers to SB-525 (PF-07055480).

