10.3.3. Recording/Reporting and Follow-Up of AE and/or SAE

AE and SAE Recording/Reporting

The table below summarizes the requirements for recording AEs on the CRF and for reporting SAEs on the Clinical Trial (CT) SAE Report Form to Pfizer Safety. These requirements are delineated for 3 types of events: (1) SAEs; (2) non-serious adverse events (AEs); and (3) exposure to the study intervention under study during pregnancy or breastfeeding, and occupational exposure.

It should be noted that the CT SAE Report Form for reporting of SAE information is not the same as the AE page of the CRF. When the same data are collected, the forms must be completed in a consistent manner. AEs should be recorded using concise medical terminology and the same AE term should be used on both the CRF and the CT SAE Report Form for reporting of SAE information.

Safety Event	Recorded on the CRF	Reported on the CT SAE Report Form to Sponsor Safety Within 24 Hours of Awareness
SAE	All	All
Non-serious AE	
Until Month 36: AllAfter Month 36: only AEs related to the study drug, or AEs with an unknown cause	None
Exposure to the study intervention under study during pregnancy or breastfeeding, and occupational exposure	None	All (And EDP supplemental form for EDP)

When an AE/SAE occurs, it is the responsibility of the investigator to review all documentation (eg, hospital progress notes, laboratory reports, and diagnostic reports) related to the event.

The investigator will then record all relevant AE/SAE information in the CRF.

It is not acceptable for the investigator to send photocopies of the participant's medical records to Pfizer Safety in lieu of completion of the CT SAE Report Form/AE/SAE CRF page.

There may be instances when copies of medical records for certain cases are requested by Pfizer Safety. In this case, all participant identifiers, with the exception of the participant number, will be redacted on the copies of the medical records before submission to Pfizer Safety.

The investigator will attempt to establish a diagnosis of the event based on signs, symptoms, and/or other clinical information. Whenever possible, the diagnosis (not the individual signs/symptoms) will be documented as the AE/SAE.

Assessment of Intensity

Intensity will be categorized by toxicity grade according to the Common Terminology Criteria for Adverse Events (CTCAE) Version 4.03.

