- The investigator may change his/her opinion of causality in light of follow-up information and send a SAE follow-up report with the updated causality assessment.
- The causality assessment is one of the criteria used when determining regulatory reporting requirements.
- If the investigator does not know whether or not the study intervention caused the event, then the event will be handled as “related to study intervention” for reporting purposes, as defined by the sponsor. In addition, if the investigator determines that an SAE is associated with study procedures, the investigator must record this causal relationship in the source documents and CRF, and report such an assessment in the dedicated section of the CT SAE Report Form and in accordance with the SAE reporting requirements.

Follow-up of AEs and SAEs

- The investigator is obligated to perform or arrange for the conduct of supplemental measurements and/or evaluations as medically indicated or as requested by sponsor to elucidate the nature and/or causality of the AE or SAE as fully as possible. This may include additional laboratory tests or investigations, histopathological examinations, or consultation with other health care professionals.
- If a participant dies during participation in the study or during a recognized follow-up period, the investigator will provide sponsor with a copy of any postmortem findings including histopathology.
- New or updated information will be recorded in the originally completed CRF.
- The investigator will submit any updated SAE data to the sponsor within 24 hours of receipt of the information.

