#### 3.1. Primary Endpoints

##### 3.1.1. Incidence of Adverse Events and Serious Adverse Events

For Years 1 to 3, all serious and non-serious AEs will be collected. For Years 4 and 5, all SAEs (regardless of relation to study intervention) and non-serious AEs determined to be related to study intervention by the investigator or where causality is unknown will be collected.

Incidence of AEs and SAEs, include clinically significant changes from pre vector dosing in:

- physical examinations;
- clinical laboratory assessments;
- immune parameters;
- vital signs;
- ECG;
- liver imaging.

Abnormal findings that meet the criteria for AE reporting in this study are to be reported as AEs, and thus will be included in the primary endpoint summary table.

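### From Month 36, non-serious complications attributed to the optional research liver biopsy fall outside the AE collection rule, and Protocol 8.3.1.2 conflicts with that rule

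*Protocol*

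**What the plan says.** Protocol 8.3.1 collects all AEs from consent onward, then narrows the scope: "from Month 36 through to the end of study (Month 60), only the following AEs will be actively collected". The list that follows has two entries, SAEs and "Non-serious AEs determined to be related to study intervention by the investigator or where causality is unknown". Protocol Section 6 defines study intervention as SB-525 and includes no study procedure in the term.

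The recording table in Protocol 10.3.3 applies the same limit to the CRF. After Month 36 the non-serious events to record are "only AEs related to the study drug, or AEs with an unknown cause". SAP 3.1.1 repeats it for Years 4 and 5: "non-serious AEs determined to be related to study intervention by the investigator or where causality is unknown will be collected". SAP 6.1.1 restates it more briefly, naming treatment-related AEs plus all SAEs.

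The optional biopsy has no matching time limit. Protocol 8.2.14 allows it "during the postinfusion period until year 5 i.e, the end of the study", says that "it can be performed at any time postinfusion to assess liver health, integration and FVIII in the liver", and permits one repeat later. The route is transjugular or percutaneous, and at least two cores are taken.

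Protocol 8.3.1.2 contains a broader instruction. It closes by telling the investigator to put on the CRF every AE that is directly observed or spontaneously reported, and that sentence has no Month 36 limit.

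**The concern.** The Month 36 restriction suits a long follow-up after a single infusion, when most unrelated minor events say little about the product. It was not adapted to an invasive research procedure that may be done inside the restricted period. Puncture-site pain or a haematoma that the investigator puts down to the biopsy has a known cause, and that cause is not SB-525. It therefore meets neither condition for collection.

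AE incidence is a primary endpoint, and the substudy is an elective procedure in people with severe hemophilia. The same complication would be an AE if the biopsy fell before Month 36, and might or might not be one if it fell later, depending on which instruction the site followed. A low count of minor biopsy complications in Years 4 and 5 could then reflect the collection rule rather than tolerability.

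**Working it through.** The documents give no figure to reproduce. The check sets the rules side by side.

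**Overlap of the two windows.** Restricted collection runs from Month 36 to Month 60 (Protocol 8.3.1), and the biopsy window runs from infusion to Month 60 (Protocol 8.2.14). Overlap = 60 − 36 = 24 months; 24 / 60 = 40% of follow-up. This is a share of calendar time, not of biopsies.

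**What happens to each kind of event after a biopsy.**

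| Event | Before Month 36 | From Month 36: Protocol 8.3.1 and 10.3.3 table | From Month 36: last sentence of Protocol 8.3.1.2, read alone |
|---|---|---|---|
| Serious, any cause | collected | collected | recorded |
| Non-serious, related to SB-525 | collected | collected | recorded if observed or reported |
| Non-serious, cause unknown | collected | collected | recorded if observed or reported |
| Non-serious, attributed to the biopsy | collected | **not collected** | recorded if observed or reported |

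Only the last row changes at Month 36, and only there do the two instructions disagree.

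**Whether another rule closes the gap.**

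- Procedure causality: Protocol 10.3.3 has a rule on events linked to study procedures, but it applies "if the investigator determines that an SAE is associated with study procedures", so non-serious events are not covered.
- Biopsy section: Protocol 8.2.14 asks that findings be followed up as medical care requires. It gives no AE recording instruction.
- Concomitant medication: Protocol 6.5 and SAP 6.5.4 carry the same post-Month-36 limit, so treatment given for such an event would not be recorded either.
- Concomitant procedures: SAP 6.5.4 records these throughout. That documents the biopsy, not its complications.
- e-Diary: Protocol 8.1.3 collects hemophilic bleeds and the FVIII used to treat them to the end of the study. A bleed after a biopsy may appear there, but not as an AE. SAP 3.2.2 leaves bleeds associated with a surgical procedure out of treated ABR and does not say whether a biopsy counts as one.
- Biopsy reporting: SAP 6.3.6 plans mainly a description of the findings of each biopsy and does not mention AEs.

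**Number of events.** This would be (biopsies after Month 36) × (rate of non-serious complications attributed to the biopsy) × (proportion a site leaves off the CRF). The documents give none of the three. SAP 6.3.6 says only that few participants will have a biopsy, in a study of about 20.

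**The case against.** The strongest counter-argument is Protocol 8.3.1.2. It requires non-serious AEs in the active collection period to be recorded, and Protocol 8.3.1 defines that period as running to Month 60. It then asks for every observed or spontaneously reported AE. Participants stay under hospital observation after the biopsy, so early pain or haematoma would often be seen or mentioned. On this reading Protocol 8.3.1 limits active questioning, not recording. This has force, and it means that nil capture is not established. It does not remove the gap: 8.3.1.2 refers back to 8.3.1 for its scope, and the 10.3.3 table limits what goes on the CRF after Month 36. Sites hold two instructions that point in different directions.

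Other points also stand. Serious complications are collected to Month 60, and the SAE definition is broad, covering hospitalization and important medical events. SAP 6.6.1 calls for footnotes stating which types of AE were collected in each period, so a reader of the tables would know that collection was restricted. That discloses the restriction but does not recover the events. The primary safety objective also concerns SB-525, and events known to be due to a biopsy say little about it. Their main value is for the safety record of the substudy.

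A reader might infer that the Years 4 and 5 record will show no non-serious biopsy complications whatever happens. Protocol 8.3.1.2 and the e-Diary do not support that. A reader might also infer that the DMC or later participants will lack these data. That depends on the DMC charter, CRF instructions and consent text, which are not in the documents reviewed.

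**Conclusion.** The gap is real but narrow. From Month 36, non-serious AEs that the investigator attributes to the optional biopsy fall outside Protocol 8.3.1, the 10.3.3 table, SAP 3.1.1 and SAP 6.1.1, while Protocol 8.3.1.2 can be read to include them. Capture would be inconsistent between sites and across the Month 36 boundary. Events that are serious, related to SB-525 or of unknown cause are not affected, and neither is anything before Month 36.

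The conclusion rests on Section 6's definition of study intervention and on the investigator being confident that the biopsy was the cause. It needs no assumption about biopsy numbers or complication rates. The overlap is 24 of 60 months. The number of events at risk is small and cannot be estimated from the documents, so no probability is attached to it. The case for correcting it is that the inconsistency concerns the safety record of an elective invasive procedure and is cheap to remove.

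**What to change.** - In Protocol 8.3.1, the Protocol 10.3.3 table, SAP 3.1.1 and SAP 6.1.1, add that from Month 36 non-serious AEs which the investigator considers related to a study procedure, including the optional liver biopsy, are also collected.
- Align Protocol 8.3.1.2 with the amended 8.3.1, so that sites have one statement of what is recorded after Month 36.
- Extend the post-Month-36 concomitant-medication rules in Protocol 6.5 and SAP 6.5.4 to cover treatment given for these events.
- In SAP 6.3.6, add a listing of the AEs that follow each biopsy, with relation to the procedure.

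The cost is one added bullet with matching text in both documents, a relation-to-procedure field for non-serious AEs, and a few extra AE and medication records among participants who have a biopsy. No visit or procedure is added. Events already missed under the current wording could be recovered only as far as source notes allow.

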8.3.1.1. Reporting SAEs to Pfizer

All SAEs, occurring in a participant during the active collection period as described in Section 8.3.1 are reported to Pfizer Safety on the CT SAE Report Form immediately upon awareness and under no circumstance should this exceed 24 hours, as indicated in [Appendix 3](#) (Section 10.3). The investigator will submit any updated SAE data to the sponsor within 24 hours of it being available.

8.3.1.2. Recording Nonserious AEs and SAEs on the CRF

All nonserious AEs and SAEs occurring in a participant during the active collection period as described in Section 8.3.1 are recorded on the CRF. AEs and SAEs that begin after obtaining

informed consent but before the start of study intervention will be recorded on the Medical History/Current Medical Conditions section of the CRF, not the AE section. AEs and SAEs that begin after the start of study intervention are recorded on the AE section of the CRF.

The investigator is to record on the CRF all directly observed and all spontaneously reported AEs and SAEs reported by the participant.

